### 5.1 Clinical Performance Endpoint

Clinical performance will be determined by the interventional cardiologist clinical operator based on a 5-point Likert-scale rating evaluation following each PCI case. The rating evaluation includes the following four categories, with individually scored criteria as listed, which are consistent with the Vis-Rx Prime Catheter product specifications:

Category 1, Preparation:

- Ease of handling product packaging.
- Ease of making PIM-catheter connection.
- Ease of purging.

Category 2, Deliverability:

- Ease of loading onto the guidewire.
- Ease of navigation to imaging region.
- Visibility of radiopaque markers.
- Ease of withdrawal over guidewire.

Category 3, Image Quality:

- Lumen visualization.
- Stent visualization.
- Overall image quality.

	Title: Vis-Rx Prime Micro-Imaging Catheter Clinical Evaluation Study – Clinical Investigation Plan	Document No. MISC-074
	Page 15 of 28	Revision: C

Category 4, Overall Performance:

- Image acquisition workflow (pullback).
- Console screen layout.
- Overall ability to visualize and assess acquired images.

The above criteria will be graded on the following 5-point Likert Scale as evaluated by the interventional cardiologist clinical operator:

5: Excellent; 4: Good; 3: Acceptable; 2: Poor; 1: Unacceptable.

The objective is a mean score above 3 for each of the four categories defined above.

## 5.2 Technical Performance Endpoint

Technical performance will be determined by an objective measurement of image clarity performed on the acquired HF-OCT pullback images by an independent core lab following the PCI case. The technical endpoint is the length measurement of image clarity in each pullback, known as the Clear Image Length (CIL, in millimeters). The objective is that pullbacks acquired in this evaluation have a median CIL greater than 35 mm.

The 35 mm target CIL arises from the following factors:

1. Average lesion length:  
The average atherosclerotic lesion length is 17 mm, with a standard deviation of 4 mm per the citations, which included an analysis of over 100,000 patients.
2. Standard deviation of lesion length:  
Two standard deviations (8 mm) have been added to the average lesion length to account for 98% of the lesions likely to be imaged using HF-OCT in the enrolled subject population.
3. Landing zones:  
Intracoronary imaging convention for PCI procedures involves imaging “landing zones” or “reference segments” of healthy vessel distal and proximal to the target atherosclerotic lesion prior to treating with stent implantation. The assessment and measurements performed on these 5 mm long landing zones often help determine the size of the stent implanted in the lesion. Therefore, the goal is to acquire a clear image of both the distal and proximal landing zones in the HF-OCT pullback image.
4. Calculation of CIL objective:  
 $17 \text{ mm} + 2 \times (4 \text{ mm standard deviation}) + 2 \times (5 \text{ mm landing zone}) = 35 \text{ mm}.$

Participating subjects are anticipated to have an average of 1.6 implanted stents per the meta-analysis cited previously. Key results from this meta-analysis are excerpted:

- Angiographic features of included patients 150 arms with 102,735 patients.
- Length of lesion in mm (median  $\pm$  SD)  $17 \pm 4$ .
- Number of stents for patients (median, min–max) 1.6 (1–2).

Participating clinical operators might use the Gentuity HF-OCT imaging technology to assess more than one atherosclerotic lesion in participating subjects, thereby imaging more lesions or vessels with HF-

	Title: Vis-Rx Prime Micro-Imaging Catheter Clinical Evaluation Study – Clinical Investigation Plan	Document No. MISC-074
	Page 16 of 28	Revision: C

OCT than there are subjects enrolled in this evaluation. Furthermore, each lesion can be imaged with HF-OCT multiple times throughout the PCI procedure, beginning with pre-intervention to visualize the lesion characteristics, later post-intervention following stent deployment to assess stent expansion and determine if stent struts are well-apposed to the vessel wall, and to determine if further stent expansion is necessary. The number of HF-OCT pullbacks performed in an eligible lesion is at the discretion of the operator and in consideration of intravascular imaging guidelines. It is therefore expected that this evaluation will collect more HF-OCT pullback images than enrolled subjects. This will provide an adequate sample of HF-OCT pullback images for CIL statistical analysis in the target patient population (Section 7.2).

Following the conclusion of each PCI case, the acquired HF-OCT pullback images will be anonymized and transferred to an independent core lab experienced in analysis of clinical intracoronary HF-OCT pullback images. The core lab will analyze each HF-OCT pullback according to pre-determined criteria for image clarity, and each pullback will receive a CIL score.

### 5.3 Safety Endpoint

Safety will be determined based on adverse event data. The primary endpoint for safety is the incidence rate for each HF-OCT Imaging procedure related adverse event observed in the study. The overall rate and severity of adverse events will be analyzed based on the total number of catheters used for the HF-OCT procedures performed. Design of the Evaluation

### 5.4 General

This is a prospective, single-arm, unblinded, multi-center clinical evaluation assessing the safety and imaging capabilities of the Gentuity High-Frequency Optical Coherence Tomography (HF-OCT) System and the Vis-Rx Prime Micro-Imaging Catheter for use in PCI procedures.

The evaluation will be conducted at 3 to 5 centers and will enroll between 30 and 70 subjects who will undergo HF-OCT imaging. A conservative estimate of the number of achieved pullbacks was used to test the robustness of the statistical model. In this case, each subject is expected to yield 1.3 imaging pullbacks during the PCI procedure (as compared with an expected mean of 1.6 stents per patient from Section 5.2), for an expected total of at least 39 HF-OCT imaging pullbacks in the evaluation. The sample will reflect a range of clinical operators as well as patients and vessels consistent with the labeling for the device.

The clinical performance endpoint is the 5-point Likert scale rating by the interventional cardiologist clinical operator following each PCI case. The objective is a mean rating of greater than 3 for each of the four categories, where 3 is considered acceptable. Refer to section 5.1 for further details of the clinical performance evaluation.

The technical performance primary endpoint is that the acquired HF-OCT pullback images have a median Clear Image Length (CIL) of greater than 35 mm, as measured by an independent core lab experienced in analysis of intracoronary HF-OCT images. The target of 35 mm CIL is based on the

	Title: Vis-Rx Prime Micro-Imaging Catheter Clinical Evaluation Study – Clinical Investigation Plan	Document No. MISC-074
	Page 17 of 28	Revision: C

average and standard deviation of atherosclerotic lesion length and the convention of imaging a distal and proximal landing zone that serves as a reference of the neighboring healthy vessel.

## 5.5 Devices

The Gentuity High-Frequency Optical Coherence Tomography (HF-OCT) Imaging System Console and the Vis-Rx Prime Micro-Imaging Catheter are the devices subject to evaluation. Please, refer to Section 2.2 of this evaluation protocol for further details. There are no comparator or control devices in this evaluation. Other medical devices may be used as part of PCI standard-of-care at the discretion of the interventional cardiologist clinical operator, including guidewires, stents, angioplasty balloons, etc.; none of these devices shall be investigational or involved in another clinical study or evaluation.

## 5.6 Subjects

In general, this evaluation is intended to enroll “all comers” for standard-of-care PCI treatment procedures who also meet the Indications for Use for the Gentuity HF-HF-OCT Imaging System and Vis-Rx Prime Micro-Imaging Catheter at the participating centers during the time of subject screening and enrollment. The subjects eligible for enrollment and participation in this clinical evaluation are those that meet all the below inclusion criteria, none of the below exclusion criteria, and who provide written informed consent for participation prior to their PCI procedure. The evaluation inclusion and exclusion criteria are aligned with the cleared Indications for Use, repeated here:

The Gentuity HF-OCT Imaging System with Vis-Rx Prime Micro-Imaging Catheter is intended for intravascular imaging and is indicated for use in coronary arteries in patients who are candidates for transluminal interventional procedures. The Vis-Rx Prime Micro-Imaging Catheter is intended for use in vessels 1.3 to 6.0 mm in diameter. The Vis-Rx Prime Micro-Imaging Catheter is not intended for use in a target vessel that has undergone a previous bypass procedure.

### 5.6.1 Inclusion Criteria

The subjects who are screened and enrolled should meet all the following inclusion criteria:

- Patients 18 years of age, or older.
- Patients willing and able to provide written informed consent to participate in evaluation.
- Patients who are candidates for transluminal interventional procedures for their coronary arteries (also known as PCI).

### 5.6.2 Exclusion Criteria

The subjects who are screened and enrolled should have none of the conditions, history, or anatomy as described in the following general exclusion criteria, which are contraindications of the Gentuity HF-OCT Imaging System and Vis-Rx Prime Micro-Imaging Catheter according to the instructions for use.

- Bacteremia or sepsis.
- Major coagulation system abnormalities.
- Severe hemodynamic instability or shock.
- Acute renal failure.

[figure not shown]
	Title: Vis-Rx Prime Micro-Imaging Catheter Clinical Evaluation Study – Clinical Investigation Plan	Document No. MISC-074
	Page 18 of 28	Revision: C

- Disqualified for Coronary Artery Bypass Graft (CABG) surgery.
- Disqualified for PCI procedure.
- Patients currently enrolled in another study to evaluate an investigational device or medication.
- Any target vessel which has undergone a bypass procedure.

#### 5.6.2.1 Lesion-specific exclusion criteria

Enrolled subjects will be screened for lesion-specific exclusion criteria during the PCI procedure using diagnostic angiography. Subjects that undergo HF-OCT imaging and target atherosclerotic lesions that are imaged should have none of the following lesion-specific conditions or anatomy, which are contraindications of the Gentuity HF-OCT Imaging System and Vis-Rx Prime Micro-Imaging Catheter according to the Instructions for Use.

- Total occlusion.
- Coronary artery spasm.
- Large thrombus (as visible under angiography).

**Figure 3:** Participating subject procedural flow chart, from informed consent through study exit, including post-PCI data collection and image analysis.

	Title: Vis-Rx Prime Micro-Imaging Catheter Clinical Evaluation Study – Clinical Investigation Plan	Document No. MISC-074
	Page 19 of 28	Revision: C

### 5.6.3 Duration of Participation

Each participating subject is expected to be in the evaluation from the time of providing written informed consent through the course of their PCI procedure. Details on the point of enrollment, evaluation exit, and withdrawal are all described in the sections below. The progression of a subject's participation in the evaluation is shown in the flow chart described in **Figure 3**.

### 5.6.4 Point of enrollment

Patients will be considered enrolled in this clinical evaluation if –

- a) Written informed consent has been obtained, AND
- b) The patient meets all the inclusion criteria, none of the general exclusion criteria and none of the lesion-specific exclusion criteria after diagnostic angiography.

Patients that do not qualify for the study based on the inclusion/exclusion criteria will be considered screen failures.

### 5.6.5 Primary Analysis Population

Several exclusion criteria apply to characteristics of the target lesion(s) which can only be assessed and confirmed during the PCI following the diagnostic angiography. Only subjects who undergo HF-OCT imaging will be included in the Primary Analysis Population. The start of the HF-OCT imaging procedure is considered the introduction of the Vis-Rx Prime Imaging Catheter into the hemostatic valve which corresponds to its insertion into the subject's bloodstream.

Any patient that is consented and screened, but who does not undergo the HF-OCT imaging procedure, will not be included in the Primary Analysis Population.

The evaluation will include between 30 and 70 HF-OCT imaged subjects in the Primary Analysis Population.

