## 6 Statistical Analysis Plan

### 6.1 Introduction

The study features a prospective, single arm, unblinded, multi-center design. The study will enroll between 30 and 70 subjects who will undergo HF-OCT imaging at 3-5 participating centers. The objective of this study is to evaluate the clinical and technical performance in the target patient population. The clinical performance will be measured by the operator's subjective evaluations of catheter preparation, catheter deliverability, overall catheter ease of use, and image quality. The technical performance will be measured by an objective measurement of the length of clarity in each HF-OCT pullback or Clear Image Length (CIL, in millimeters).

The Gentuity HF-OCT can capture up to 100 mm of vessel segment in a single pullback. The study's primary hypothesis states that the true population median CIL is greater than the reference standard of

	Title: Vis-Rx Prime Micro-Imaging Catheter Clinical Evaluation Study – Clinical Investigation Plan	Document No. MISC-074
	Page 21 of 28	Revision: C

35 mm, such that a one-sample comparison of median to a reference CIL standard or  $\mu_0$  can be expressed as the following:

$H_0: \mu = \mu_0$  vs.  $H_1: \mu \neq \mu_0$ , where  $\mu_0 = 35$  mm was chosen per the analysis of Section 5.2

The test will be accomplished by a one-sample two-sided exact Wilcoxon signed-rank test with 0.05 type I error rate. The data support  $\mu > \mu_0$  if the two-sided p-value is less than 0.05 and the estimate of  $\mu$  is greater than  $\mu_0$ .

For all enrolled subjects who are included in the Primary Analysis Population, clinical data, and collected HF-OCT images will be retained and analyzed for technical performance. For subjects who were consented and enrolled but who were screening failures during the PCI procedure via lesion-specific exclusion criteria, any clinical data collected prior to PCI will not be included in the evaluation demographic, medical history, or PCI details analyses.

For all enrolled subjects and cases that involve HF-OCT imaging, the clinical operator will be interviewed to evaluate the Gentuity HF-OCT technology for its clinical performance in catheter preparation, catheter deliverability, image quality, and overall performance.

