### 6.5 Clinical Performance Analysis

The performance endpoints consist of the following four previously identified categories (Section 5.1):

- Catheter preparation
- Catheter deliverability
- Image quality
- Overall performance

Subjective criteria within these categories will be evaluated and rated using the 5-point Likert scale by the interventional cardiologist clinical operator. The performance endpoints will be analyzed by mean and standard deviation. As the Likert scale evaluation will be conducted following the PCI case of each enrolled subject, the performance evaluation sample will be equivalent to the number of enrolled

	Title: Vis-Rx Prime Micro-Imaging Catheter Clinical Evaluation Study – Clinical Investigation Plan	Document No. MISC-074
	Page 23 of 28	Revision: C

subjects who underwent HF-OCT imaging. The primary performance objective is to achieve a mean rating of greater than 3 (or acceptable) for the above four categories. No inferential statistical analysis will be performed for these clinical performance endpoints.

Three (3) to five (5) centers will enroll subjects, and there may be multiple interventional cardiologist clinical operators at each participating center. Therefore, there will be a range of clinical operators who evaluate the performance of the Gentuity HF-OCT Imaging System and Vis-Rx Prime Catheter in a range of PCI cases.

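### Preparation and guidewire-loading ratings are analysed only where a catheter was inserted, so cases abandoned at those steps drop out of the means that judge them

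*Combined protocol and SAP*

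**What the plan says.** The clinical performance endpoint (section 5.1) is a 5-point operator rating in four categories. The objective is a mean above 3 in each, and section 6.5 plans no inferential analysis. Preparation has three items: packaging, "Ease of making PIM-catheter connection", and purging. Deliverability has four: loading onto the guidewire, navigation, marker visibility and withdrawal.

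The following passages decide who is rated and analysed:

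- Section 5.6.4: enrollment requires consent and eligibility, including "none of the lesion-specific exclusion criteria after diagnostic angiography". It is therefore complete before insertion.
- Section 5.6.5: "The start of the HF-OCT imaging procedure is considered the introduction of the Vis-Rx Prime Imaging Catheter into the hemostatic valve". A patient "who does not undergo the HF-OCT imaging procedure, will not be included in the Primary Analysis Population".
- Section 6.1: "For all enrolled subjects and cases that involve HF-OCT imaging, the clinical operator will be interviewed".
- Section 6.5: "the performance evaluation sample will be equivalent to the number of enrolled" and, continuing after a page break, "subjects who underwent HF-OCT imaging". The same sentence opens more widely: "As the Likert scale evaluation will be conducted following the PCI case of each enrolled subject".

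Section 6.3 uses observed data only, without imputation. Section 6.8 collects device malfunctions at setup and during use on a separate form. No rule links that form to the category means.

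**The concern.** For the items that precede insertion, being counted depends on having got through the step being rated. If the catheter cannot be connected, purged or loaded, and no other catheter is inserted, the subject is enrolled but outside the analysed sample. The cases lost are the ones that would score worst on these items.

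The objective is a bare point estimate compared with 3, with no interval or test beside it, so the choice of analysis set carries the whole result. The steps also bear on what is new in this device. Section 2.2 describes a modified rapid exchange tip meant to help delivery over the guidewire, and section 1.2 says that the redesign is mainly to cut manufacturing and material costs. The data are intended for a European submission, where an assessor may well ask what became of catheters opened but not inserted.

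**Working it through.** **The plan's own figures.** The plan states no expected rating, failure rate or sample size for this endpoint. Its only power calculation is for Clear Image Length (section 6.2). The row with effect 10 mm and SD 17 mm reproduces: a two-sided one-sample t-test with 25 observations has 80.56% power (stated 80.6%), and 25/(2/3) = 37.5, rounded up to 38. Nothing below depends on it.

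**Order of steps.** The imaging steps (5.6.8, under 5.7) put catheter preparation third and positioning in the vessel fifth. Loading onto the wire must come before entry through the valve. So 3 Preparation items and 1 Deliverability item, 4 of the 13 rated items, precede the gate. Navigation, marker visibility and withdrawal follow it.

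**Effect on the Preparation mean.** Let n be the rated cases (30 to 70, section 5.6.5), m their mean, and k the abandoned cases. The values of m and k are assumptions.

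If each abandoned case scores 1 on every Preparation item, the mean over all attempted cases is (n·m + k)/(n + k). It reaches 3 or less once k ≥ n(m − 3)/2.

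| Assumed m | k needed, n = 30 | k needed, n = 70 |
|---|---|---|
| 3.2 | 3 | 7 |
| 3.3 | 5 | 11 |
| 3.5 | 8 | 18 |
| 4.0 | 15 | 35 |
| 4.5 | 23 | 53 |

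- n = 30, m = 3.3, k = 5: (99 + 5)/35 = 2.97, objective missed.
- n = 30, m = 4.0, k = 3: (120 + 3)/33 = 3.73, objective met.
- n = 30, m = 4.0, k = 15: (120 + 15)/45 = 3.00, not above 3.

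**If only the failed step scores 1.** Keep n = 30, m = 3.3 and k = 5, rate completed steps 3.3, leave later steps unrated, and average within each case first:

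- Failure at the third step: case mean (3.3 + 3.3 + 1)/3 = 2.53; overall (99 + 5 × 2.533)/35 = 3.19.
- Failure at the second step: case mean (3.3 + 1)/2 = 2.15; overall (99 + 5 × 2.15)/35 = 3.14.
- Failure at the first step: case mean 1; overall 2.97.

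The plan does not say whether a category mean averages case means or pools items. With pooling, even failure at the first step gives (90 × 3.3 + 5)/95 = 3.18.

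**Effect on Deliverability.** A loading failure can be scored on one item of four. With n = 30, m = 4.0 and k = 3, pooling items gives (4 × 30 × 4.0 + 3)/(4 × 30 + 3) = 483/123 = 3.93. Setting the case mean to 1 gives 3.73.

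**The case against.** The case on the other side is substantial.

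- A reader might infer that a catheter failing in preparation or loading can never count. The documents do not support that. If a second catheter is inserted, the case is rated, and nothing stops the operator from marking Preparation down for the first. Difficulty short of failure also counts. What stands is that the plan does not say how such a case is to be rated, and that cases with no catheter inserted are lost.
- A reader might infer that no rating is taken in abandoned cases. Section 6.5 leaves this open: its opening clause ties the rating to every enrolled subject, and its next clause counts only imaged ones. A rating might be taken and then left out. That is an inconsistency to settle, and it does not restore the case to the analysed sample.
- A reader might extend the point to all of Deliverability. The gate is the hemostatic valve, not a successful pullback, so a catheter that enters but cannot be navigated stays in. Only the loading item is exposed.
- Setup failures are not hidden. Section 6.8 and the schedule of assessments capture malfunctions, and the synopsis sends them to complaint handling. They simply do not reach the endpoint.
- The endpoint is subjective and descriptive, and the primary hypothesis concerns Clear Image Length. This limits the stakes.
- Figure 3 and the case report forms are not available here, so a rule on setup failures may exist there. None appears in the text.

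**Conclusion.** The point holds for a narrow group: enrolled subjects in whom preparation or loading failed and no catheter was inserted. Their absence can move the Preparation mean and the loading item only upward, on the assumption that a failed step would be rated below the average of the rest.

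The size cannot be computed from the documents. The pass or fail result is fragile only if ratings are modest and such cases are frequent. The 2.97 result needs a mean of 3.3, abandonment in 5 of 35 attempted cases (14%), and a score of 1 on every Preparation item or, with averaging by case, failure at the very first step. If a later step fails and only that step scores 1, the mean is 3.14 to 3.19 and the objective is met. At a mean of 4.0, abandonment would have to reach 15 of 45 attempted cases (33%), all scored 1 throughout. To say that the objective would be met because failures were left out therefore goes further than the documents allow. What they do support is that any such failure makes the reported means too favourable.

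**What to change.** In sections 5.6.5, 6.1 and 6.5, for the three Preparation items and the guidewire-loading item, define the analysis set as every enrolled subject for whom a Vis-Rx Prime catheter was opened for use. The operator rates each step attempted, and the rating takes in any catheter that failed as well as the one finally used. Steps not attempted stay unrated, so a subject stopped for reasons unrelated to the catheter contributes only the steps that took place. Bring the two clauses of the section 6.5 sentence into line with this, and state how item scores form a category mean.

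Keep the imaged-only means as secondary. Report setup failures per catheter opened beside the means. Add a sensitivity analysis that scores an attempted but uncompleted step as 1. A forced score overrides the operator's judgement, so it belongs in a sensitivity analysis and not in the main result.

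The cost is wording in three sections and one extra line on the rating form; setup malfunctions are already collected and no patient procedure is added. The means may come out slightly lower.
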